9.7.1.3 TEAEs Leading to Treatment Discontinuation, Treatment Interruption, Death

The number of subjects and exposure-adjusted event rate for TEAEs leading to treatment discontinuation, TEAEs leading to treatment interruption, and TEAEs leading to death will be summarized by SOC/PT for Safety Set during 110 TE Period.

In addition, the following listings will be provided for Safety Set during 110 TE Period:

- Listing of TEAEs leading to treatment discontinuation
- Listing of TEAEs leading to treatment interruption
- Listing of AEs leading to death
- Listing of Serious AEs
- Listing of all AEs by subject
- Listing of TEAEs by preferred term

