worst/highest relationship level in the relationship summaries. An AE overview table will be provided. A separate table will summarize all TEAEs when each of them is considered unique, hereafter referred to as an AE count table. In addition, a listing containing individual subject AE data for all deaths and other serious and significant AEs will be provided separately. All AEs, including pre- and post-treatment AEs, will be presented in individual subject data listings.

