13.1.2.2 Documentation of Serious Adverse Events

For the Treatment Cohorts, all SAEs that occur after obtaining informed consent and assent (where applicable) through the Safety Follow-up Visit, regardless of causality, will be reported by the investigator to Vertex GPS. In addition, all SAEs that occur after the Safety Follow-up Visit and are considered related to study drug(s) will be reported to Vertex GPS **within 24 hours**.

For the Observational Cohort, all related SAEs that occur after obtaining informed consent and assent (where applicable) through the Long-term Follow-up telephone contact at Year 2 will be reported by the investigator to GPS within 24 hours.

SAEs will be recorded on the Vertex Organized Safety Information Collection Form (hereafter referred to as the “SAE Form”) using a recognized medical term or diagnosis that accurately reflects the event. SAEs will be assessed by the investigator for relationship to the investigational study drug(s) and possible etiologies. On the Clinical Trials SAE Form, relationship to study drug(s) will be assessed only as related (includes possibly related) or not related (includes unlikely related), and severity assessment will not be required. For the purposes of study analysis, if the event has not resolved at the end of the study reporting period, it will be documented as ongoing. For purposes of regulatory safety monitoring, the investigator is required to follow the event to resolution and report to Vertex the outcome of the event using the Vertex Clinical Trials SAE Form.

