- Derivations of measurements at scheduled visits per specified visit windowing rules;
- Derivations of baseline/last on-treatment measurements;
- Derivations of the maximum/minimum on-treatment values and maximum/minimum changes from baseline values for safety analyses;
- Data listings where appropriate.

Treatment-emergent (TE) Period will include the time from the first active dose of VX-661/ivacaftor or ivacaftor alone (in the parent study or Study VX14-661-110, but after the washout period, if applicable) to the Safety Follow-up Visit in Part A or 28 days after the last dose of the study drug for subjects who do not have a Safety Follow-up Visit or who have their Safety Follow-up Visit more than 35 days after the last dose in Part A of Study VX14-661-110. For subjects who participate in another qualified Vertex study before completing Part A of Study VX14-661-110 (96 weeks) and re-enroll in Study VX14-661-110, the TE Period will exclude the time spent in the other study.

110 Treatment-Emergent (TE) Period is defined as the time from 1st dose of study drug in Part A to SFU in Part A or 28 days after the last dose of the study drug for subjects who do not have a SFU Visit or who have their SFU Visit more than 35 days after the last dose in Part A. For subjects who participate in another qualified Vertex study before completing Part A (96 weeks) and re-enroll in Study 110, the TE Period will exclude the time spent in the other study. The **efficacy analysis baseline** is defined as the most recent non-missing measurement (scheduled or unscheduled) collected prior to the first dose of study drug in the parent studies for all subjects, except for subjects randomized to the placebo arm in Study 106.

The efficacy analysis baseline for subjects randomized to the Study 106 placebo arm is defined as the most recent non-missing measurement (scheduled or unscheduled) collected prior to the first dose of study drug in Study 110.

The **safety analysis baseline**, unless otherwise specified, is defined as the last non-missing assessment prior to the first dose of active treatment (TEZ/IVA or IVA) from the parent study (after the wash-out period, where applicable) or Study 110, whichever is earlier.

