9.7 Safety Analysis

9.7.1 Adverse Events

For each individual parent study, summary table of treatment emergent AEs during the respective parent study will be included in the Study 110 CSR. The parent studies are 103, 111, 106, 108, 107 and 109.

The analysis of Adverse Events in the rest of section 9.7.1 will be based on the Safety Set during **110 TE Period.**

For analysis purposes, AEs will be categorized as pre-treatment AEs, treatment-emergent adverse events (TEAEs), or post-treatment AEs:

- **Pretreatment AE:** any AE that started before the first dose of study drug in Part A.
- **TEAE:** any AE that increased in severity or that was newly developed at or after the first dose of study drug in Study Part A through the end of 110 TE Period.
- **Post-treatment AE:** any AE that increased in severity or that was newly developed after 110 TE Period.

For AEs with missing or partial start date, if there is no clear evidence that the AEs started (or increased in severity) before the first dose, the start date will be imputed to the first dosing date and the AE will be considered as TEAE. As an intermediate step for programming purposes, imputation rules for missing or partially missing AE start/end dates are defined in [Section 11.4](#).

TEAEs will be classified into 4 categories of relationship to the study drugs: not related, unlikely related, possibly related, related.

TEAEs will be classified into 4 categories of severity:

- **Mild (Grade 1):** Mild level of discomfort and does not interfere with regular activities
- **Moderate (Grade 2):** Moderate level of discomfort and significantly interferes with regular activities
- **Severe (Grade 3):** Significant level of discomfort and prevents regular activities
- **Life-threatening (Grade 4 and 5):** Any adverse drug experience that places the subject, in the view of the investigator, at immediate risk of death.

All the summary tables of TEAEs display counts and exposure-adjusted event rates for the Safety Set in Study 110.

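### The SAP limits the death, serious and all-AE listings to the 110 TE Period, whereas the protocol commits to listing pre- and post-treatment AEs as well

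*SAP*

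**What the plan says.** Protocol 12.3.5.1 makes two listing commitments, neither with a period limit. The first is that "a listing containing individual subject AE data for all deaths and other serious and significant AEs will be provided separately". The second is that "All AEs, including pre- and post-treatment AEs, will be presented in individual subject data listings".

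The SAP is narrower. SAP 9.7.1 sets the scope for everything that follows: "The analysis of Adverse Events in the rest of section 9.7.1 will be based on the Safety Set during" the 110 TE Period. SAP 9.7.1.3 repeats the limit over its list of listings: "In addition, the following listings will be provided for Safety Set during 110 TE Period". Six listings follow. Three are titled as TEAE listings (leading to discontinuation, leading to interruption, and by preferred term). The other three are titled as AE listings: fatal AEs, serious AEs, and "Listing of all AEs by subject".

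SAP 9.7.1 also defines a post-treatment AE as "any AE that increased in severity or that was newly developed after 110 TE Period". No visible table or listing in the SAP uses that class.

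Collection goes further than the period. Protocol 13.1.2.2 requires that "all SAEs that occur after the Safety Follow-up Visit and are considered related to study drug(s) will be reported to Vertex GPS", with no end date. The SAE definition in Protocol 13.1.2.1 takes in a death after participation if delayed toxicity is suspected.

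**The concern.** Long-term safety is the primary objective. A programmer who follows SAP 9.7.1 and 9.7.1.3 as written would apply the period filter to all six listings. The study report would then not contain the listings that the protocol promised, and the SAP gives no reason for the change.

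The events at stake are few but of a kind that a safety reader looks for one by one, above all a late death or serious event judged related to study drug. The SAP sets up the post-treatment class, and its date-imputation rules in 11.4 assign events to it. It then gives the class no output. By contrast, SAP 9.4 lists post-treatment medications with no period limit.

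**Working it through.** No sample size, power or event figure is involved, so the check compares collection with listing.

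**Inputs**
- *Start of collection:* signing of consent or assent (Protocol 13.1.1.3).
- *End of routine collection:* the Safety Follow-up Visit if there is one. Otherwise it is the earliest of several points, one of which is 28 days after the last dose (Protocol 13.1.1.3).
- *Later collection:* related SAEs after the follow-up visit (Protocol 13.1.2.2).
- *Start of the 110 TE Period:* first dose in Part A (SAP 9.1).
- *End of the 110 TE Period:* the follow-up visit, or "28 days after the last dose of the study drug for subjects who do not have a SFU Visit" or whose visit is more than 35 days after the last dose (SAP 9.1).
- *Visit window:* 28 ± 7 days, so days 21 to 35 (Protocol 8.1.1.2).

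**Comparison**

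| Event | Collected? | In the SAP's AE listings as worded? |
|---|---|---|
| AE between consent and first Part A dose | Yes | No; before the period |
| AE up to an in-window follow-up visit | Yes | Yes |
| AE up to day 28, no follow-up visit | At most to day 28 | Yes |
| AE after day 28, visit later than day 35 | Yes, through the visit | No; the period closed at day 28 |
| Related SAE or death after the follow-up visit | Yes, to the safety group | No; after the period |

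**Row by row**
1. *Pretreatment AEs.* The protocol's listing commitment names these. Its definition includes, for re-enrolling subjects, events between re-consent and the first new dose. The parent-study tables promised in SAP 9.7.1 do not fill this gap, since they cover only events that were treatment-emergent in the parent study.
2. *Visit after day 35.* The earliest such visit is day 36. The period ends at day 28, so at least 36 − 28 = 8 days of routinely collected AEs (days 29 to 36) fall outside.
3. *No follow-up visit.* Routine collection ends no later than day 28 and the period runs to day 28, so routine collection loses nothing here.
4. *Late related SAEs.* With an in-window visit the period closes between day 21 and day 35. A related SAE reported after that is post-treatment by SAP 9.7.1 and outside all six listings.

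Three kinds of recorded event therefore fall under the protocol's commitment but outside the SAP's listings: rows 1, 4 and 5 of the table.

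**The case against.** **The limit may be a drafting slip.** Three titles say AE and three say TEAE, which suggests that the AE listings were meant to be wider. That is plausible and supports an easy correction. As worded, though, the lead-in covers all six.

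**The protocol bases safety analyses on the TE Period.** Protocol 12.3.5 does say so, and the day-28 cut-off is the protocol's own rule (12.3.1). But 12.3.5.1 is the specific rule for listings, and it names pre- and post-treatment events.

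**A reader might infer that these events appear in no planned output.** The documents do not support that. An entry after 9.7.1.4 in the SAP contents is redacted, within the AE block. The listing commitments in Protocol 12.3.3 and 12.3.5.1 have not been withdrawn. A death might also appear as a reason in the disposition listing of SAP 9.2, although that is not an AE listing.

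**A reader might infer that these events are the study's only post-treatment safety information,** because no one enrolled in the Observational Cohort (SAP 6.2). That is also too strong. The TE Period already holds about four weeks off drug, with AEs, laboratory tests, ECGs, vital signs and oximetry at the follow-up visit.

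**A reader might apply an assumed risk to all 1,044 enrolled subjects.** The documents give no rate for late events or late visits. The denominator would also be wrong. Subjects who continue into Part B have no Part A follow-up visit (SAP Figure 6-1, note d). Those moving to commercial drug need none, nor do those who enter another qualified study in time (Protocol 8.1.1.2).

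**Removing a filter may not reach the late SAEs.** This stands. Protocol 13.1.2.2 sends them to the safety group on the SAE Form, and nothing says that they enter the eCRF data behind the listings. The fix has to name their source.

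**Conclusion.** The mismatch is real and confined to listings. As worded, the SAP's death, serious and all-AE listings omit pretreatment AEs, AEs after day 28 when the follow-up visit is later than day 35, and related SAEs or deaths reported after the 110 TE Period.

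The number of events is unknown and probably small. Routine collection stops at the follow-up visit, and a visit after day 35 is already outside the protocol window. No TEAE table, exposure-adjusted rate or efficacy result changes. Late related SAEs still reach the sponsor's safety group, so the gap is in planned reporting and not in collection.

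The conclusion assumes that the period limit in SAP 9.7.1 and 9.7.1.3 is applied literally and that the redacted SAP entry does not supply these listings. It is worth correcting because the listings serve the primary objective and the correction is cheap.

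**What to change.** In SAP 9.7.1.3, keep the limit to the 110 TE Period only for the three listings titled TEAE. For the listings of fatal AEs, serious AEs and all AEs by subject:
- include every recorded AE, flagged pretreatment, treatment-emergent or post-treatment, with days since last dose;
- exempt these three listings from the general period limit in SAP 9.7.1;
- state that related SAEs reported to the safety group after the Safety Follow-up Visit are included, from the safety database if they are not in the eCRF.

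The cost is a few sentences in the SAP, a filter removed from three listings, and two added columns. If late SAEs are held only in the safety database, an extract or reconciliation step is also needed. No new assessment of subjects is required.

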9.7.1.4 Elevated Transaminase, Respiratory Events or Symptoms

Respiratory events (including symptoms) are defined as any of the following 7 TEAE PTs: Chest Discomfort, Dyspnoea, Respiration abnormal, Asthma, Bronchial hyperreactivity, Bronchospasm, Wheezing.

Respiratory symptoms are defined as any of the following 3 TEAE PTs: Chest Discomfort, Dyspnoea, Respiration abnormal.

Elevated transaminase is defined as the occurrence of any of the following TEAE preferred terms: Alanine aminotransferase abnormal, Alanine aminotransferase increased, Aspartate aminotransferase abnormal, Aspartate aminotransferase increased, Transaminases abnormal, Transaminases increased, Liver function test abnormal, Liver function test increased, Hypertransaminasaemia, Hepatic enzyme abnormal, Hepatic enzyme increased.

A summary of elevated transaminase, respiratory events and respiratory symptoms counts and exposure-adjusted event rate will be presented by PT for Safety Set during 110 TE Period.

9.7.2 Clinical Laboratory Values

With the threshold criteria for abnormal high/abnormal low listed in [Section 11.3](#), the following summaries for chemistry, LFT, hematology, coagulation, vitamin levels, and lipid panel assessments will be presented for Safety Set during 110 TE Period:

- Raw values and change from baseline will be summarized using SI units by visit.
- Number and percentage of subjects with abnormal assessments meeting the threshold criteria will be summarized during the entire 110 TE Period.
- A summary table for the shift from baseline to post-baseline will be summarized by visit.

Mean value at each visit will be plotted for each LFT parameter.

A listing containing individual subject laboratory assessment values outside the reference ranges will be provided.

Listings of abnormal urinalysis and positive serum/urine pregnancy tests will be provided.

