12.3.5.2 Clinical Laboratory Assessments

For the treatment-emergent laboratory measurements, the raw values and change from baseline values of the continuous laboratory parameters will be summarized in SI units at each scheduled time point during the TE Period. Mean value at each visit will be plotted for each of the liver function parameters. In addition, a listing containing individual subject laboratory assessment values outside the reference ranges will be provided.

The number and percentage of subjects with at least 1 threshold analysis event during the TE Period will be summarized for selected laboratory parameters. The shift of the threshold analysis criteria from baseline to postbaseline will also be summarized for selected laboratory parameters. The threshold analysis and parameter-selection criteria will be provided in the SAP.

Results of abnormal urinalysis and positive serum/urine pregnancy tests will be listed in individual subject data listings only.

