9 STATISTICAL ANALYSIS

9.1 General Considerations

Continuous variables will be summarized using the following descriptive summary statistics: the number of subjects (n), mean, standard deviation (SD), median, minimum value (min), and maximum value (max).

Categorical variables will be summarized using counts and percentages.

Visit Windowing Rules: [Section 11.1](#) defines the windows for protocol-defined visits. Note, spirometry assessments, BMI, weight, and height will be used for both efficacy and safety purposes. Their measurements will follow the visit windowing rules for efficacy parameters.

The windows will be applied for both scheduled and unscheduled visits. If no measurement is available within a visit window, the assessment will be considered missing for the visit. If there is more than one measurement available within the same visit window, the following rules will be used:

For all safety parameters, if there are multiple measurements within a visit window, then

- The record closest to the target day will be used, with the exception of the threshold analysis in which the worst record will be used.
- If there are multiple records within the same distance of the target day, the latest record will be used.
- The SFU visit will not be windowed; instead, the nominal visit will be used in relevant analyses.

For all efficacy parameters, if there are multiple measurements within a visit window, the record at the scheduled visit will be used. Otherwise,

- If there are multiple records with the same distance to the target day, the latest record will be used.
- If there are no measurements at the scheduled visit, then the record closest to the target day will be used.

- Assessments at the Early Treatment Termination (ETT) Visit will follow the windowing rules for regular visits.
- Assessments at SFU Visit will follow the windowing rules for regular visits if they fall within the upper boundary of the window for the last scheduled visit. If assessments occur after the upper boundary of the window for the last scheduled visit, they will be still considered as the SFU Visit.

Incomplete/Missing data will not be imputed, unless otherwise specified.

Outliers: No formal statistical analyses will be performed to detect or remedy the presence of statistical outliers, unless otherwise specified.

Unscheduled **Visits:** Unscheduled visit measurements will be included in the following:

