9.7.5 Pulse Oximetry

The raw values and change from baseline values will be summarized at each scheduled visit for Safety Set during 110 TE Period for the percent of oxygen saturation by pulse oximetry. The number and percentage of subjects with shift changes from baseline (normal/missing and low according to the reference range) to the lowest percent of oxygen saturation during the entire 110 TE Period will be tabulated.

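### The SAP's laboratory tables do not give the number of subjects who newly met, or worsened to, a threshold band over the whole 110 TE Period

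*SAP*

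**What the plan says.** SAP 9.7.2 applies the criteria of SAP 11.3 to the laboratory panels in the Safety Set and plans three summaries:

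- By-visit values: "Raw values and change from baseline will be summarized using SI units by visit".
- Threshold count: "Number and percentage of subjects with abnormal assessments meeting the threshold criteria will be summarized during the entire 110 TE Period".
- Shift: "A summary table for the shift from baseline to post-baseline will be summarized by visit".

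It adds plots of mean liver function values and a listing of values outside the reference range.

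Protocol 12.3.5.2 plans the same threshold count ("The number and percentage of subjects with at least 1 threshold analysis event during the TE Period will be summarized for selected laboratory parameters") and then a shift: "The shift of the threshold analysis criteria from baseline to postbaseline will also be summarized for selected laboratory parameters". That sentence neither limits the shift to visits nor says that the worst value is used.

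Two definitions in SAP 9.1 bear on this. The safety baseline "is defined as the last non-missing assessment prior to the first dose of active treatment (TEZ/IVA or IVA) from the parent study", or from Study 110 if that dose came first, whereas the 110 TE Period starts with the first Part A dose. Where a visit window holds several safety records, the one nearest the target day is taken, "with the exception of the threshold analysis in which the worst record will be used".

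For pulse oximetry, SAP 9.7.5 plans a shift from baseline "to the lowest percent of oxygen saturation during the entire 110 TE Period will be tabulated".

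**The concern.** Laboratory values are part of the primary endpoint (Protocol 7.1, SAP 5.1), and every subject in the Treatment Cohort receives the same drug. With no concurrent untreated group, a subject's own baseline is the main reference for judging whether an abnormality arose on treatment. The one table that counts subjects over the whole period does not refer to it.

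Some subjects can be expected to start abnormal. Protocol 9.2 gives a liver test abnormality as a possible ground for exclusion only where it forced permanent discontinuation of the drug. The rule in Protocol 11.8.6 on resuming study drug compares a subject's baseline with a multiple of ULN and takes the higher, so it allows for raised baselines. If such subjects enter the threshold count, pre-existing disease appears as an on-treatment finding, and the reader cannot take it out again at subject level.

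**Working it through.** No figure in the plan needs reproducing. The check compares what each table can deliver, then illustrates with assumed rates.

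**1. What each SAP 9.7.2 table delivers**

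| Table | Time span | Uses baseline | Subjects newly abnormal over the period |
|---|---|---|---|
| Values and change | each visit | yes | no (summary statistics) |
| Threshold count | whole 110 TE Period | not stated | no |
| Shift | each visit | yes | no (each visit separately) |

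The laboratory criteria in SAP 11.3 do not close the gap. All are absolute values or limits set from ULN or LLN, and none includes a change from baseline.

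**2. Why visit rows do not add up.** Let n_v be the number newly abnormal at visit v, and N0 the number not abnormal at baseline. The number ever newly abnormal lies between max(n_v), when the same subjects recur, and min(Σ n_v, N0), when no subject recurs. SAP Table 11-1 gives chemistry and hematology 10 post-baseline visits (Day 15 to Week 96). Assume full attendance.

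- With 1% newly abnormal at each visit, the minimum is 1% and the maximum 10 × 1% = 10%. If visits were independent, it would be 1 − 0.99^10 = 9.6%.
- In subjects: SAP 6.2 gives 23 + 464 + 159 + 227 + 138 + 33 = 1,044. Assume 10% abnormal at baseline (104, leaving 940 at risk) and 2% newly abnormal per visit (0.02 × 940 ≈ 19). The same visit rows fit 19 to 190 subjects, or 940 × (1 − 0.98^10) ≈ 172 under independence. If all 104 baseline-abnormal subjects are counted, the threshold table shows between 104 + 19 = 123 and 104 + 190 = 294.
- Over assumed baseline prevalences of 5% to 20% and per-visit rates of 1% to 5%, the range of ever-new subjects runs from 8–80 (20%, 1%) to 50–500 (5%, 5%).

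**3. Effect on the threshold count.** With baseline prevalence p0, proportion r of baseline-abnormal subjects abnormal again at least once, and incidence i among the rest, the reported proportion is p0·r + (1 − p0)·i. Assume r = 0.90 and i = 0.05; neither is in the documents.

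| p0 | Reported | Reported ÷ 5% |
|---|---|---|
| 0 | 0.05 = 5.0% | 1.0 |
| 5% | 0.045 + 0.0475 = 9.25% | 1.85 |
| 15% | 0.135 + 0.0425 = 17.75% | 3.55 |
| 30% | 0.27 + 0.035 = 30.5% | 6.1 |

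The distortion vanishes as p0 approaches zero, so it belongs mainly to the bands just beyond ULN or LLN.

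**4. Which record the shift uses.** Only the threshold analysis takes the worst record in a window. The SAP does not say whether the shift table counts as threshold analysis. If it does not, a transient worst value can be counted in the threshold table and be absent from the shift.

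**5. Which baseline.** For subjects given active drug in the parent study, the safety baseline precedes that dosing, but counting starts at the first Part A dose. An abnormality that began on active drug in the parent study and persisted would therefore be classed as new in Study 110.

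**The case against.** Several parts of the other side's case stand and limit the point.

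- **Protocol shift.** A reader might infer that neither document plans a suitable table. That goes too far. Protocol 12.3.5.2 plans a shift of the threshold criteria with no by-visit limit, which would permit the missing table although it does not specify the worst value. It is the SAP, which holds the analysis details, that narrows the shift to visits.
- **By-visit information.** The shift table does show baseline abnormality and new abnormality at each visit. Together with the threshold count it also brackets the answer: with T subjects counted and B abnormal at baseline, the new subjects number between T − B and T. In the example B = 104, so T = 294 gives 190 to 294, and visit rows showing persistence would narrow this. It remains a bracket, and it does not capture worsening from one band to another.
- **No comparison group.** A reader might infer that nothing shows the background level. SAP 7.4 presents Study 106 safety results beside Part A, with a placebo group in Table 7-3. That is partial help: it is one parent study in homozygous subjects, not concurrent, and SAP 9.7.2 does not refer to it.
- **Adverse events.** Laboratory worsening judged clinically significant is recorded as an adverse event (Protocol 13.1.1.2), and SAP 9.7.1.4 summarizes transaminase terms over the period. This depends on investigator judgement and is not threshold-based.
- **ECG and vital signs.** A reader might infer the same fault throughout. SAP Tables 11-5 and 11-6 do not support that: heart rate and blood pressure have rows pairing a level with a change, PR has some, and weight is wholly change from baseline. QTc has increase rows, but none paired with its 450/470 ms limits.
- **Silence.** Neither document says outright that baseline-abnormal subjects are counted. It follows from the absence of any condition.

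**Conclusion.** The point holds for the SAP's laboratory tables. Read as written, the whole-period count includes subjects already beyond a threshold at baseline. Every laboratory table that uses baseline is by visit, so none gives the number of subjects who newly met or worsened to a band over the 110 TE Period.

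Visit rows alone leave that number open by up to a factor of 10 over 10 visits (1% to 10% in the example). The size of any overstatement in the threshold count cannot be obtained from the documents. The ratios of 1.85 to 6.1 rest wholly on assumed prevalence, persistence and incidence. A reader might take them as an estimate of inflation across the table, but nothing in the plan supports that, and such prevalences are implausible for severe bands such as ALT above 8 × ULN. This is a weakness in descriptive output on a component of the primary endpoint. It is worth correcting, and no hypothesis test depends on it.

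**What to change.** - In SAP 9.7.2, tabulate the shift from baseline threshold band to worst post-baseline band over the whole 110 TE Period, in place of or beside the by-visit shift. Alternatively, split each threshold count by baseline status, so that subjects not in that band or a worse one at baseline form their own row and denominator.
- If the by-visit shift stays, say whether it uses the worst or the closest record in the window.
- State in the table that the safety baseline precedes parent-study active dosing for subjects who received active drug there. To keep abnormalities that began in the parent study from appearing as new, show the same table also against the last value before the first Study 110 dose.
- For ECG, apply the split only to absolute rows without a paired change row, such as QTc above 450/470 ms.

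The cost is a change of SAP wording and one more table per panel, from data already collected. The second baseline adds a further version of that table where it is used.
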